2.1.6 Genetic Factors

We found that certain genetic polymorphisms of APOE, phosphodiesterase 4D, and complement were also associated with increased eCD (13, 29-31). For example, patients who have the polymorphism APOE- $\epsilon 4$ have an increased incidence of eCD. In patients with deleterious polymorphisms, eCD is also attenuated by the use of statins.

2.1.7 Mortality

We have investigated if early neurocognitive change, eCD, was predictive of other significant life events. We specifically looked at mortality as a function of the presence or absence of eCD and the interaction of statin use on mortality. Our hospital laboratory database links to the National Death Index for patient mortality information. We determined mortality information on all of our patients. In the 225 patients who had died, we obtained their date of death. Using Kaplan-Meier Analyses, we observed that those asymptomatic patients who were not taking statins who have eCD have a significantly increased risk of earlier mortality than those patients who did not have eCD. Median survival of CEA patients that exhibited eCD was 12.5 years compared with 16.5 years for patients without eCD (Log rank $P=0.06$), and five-year cumulative incidence survival proportions and 95% confidence intervals were 0.82 (0.76-0.89) and 0.86 (0.83-0.90), respectively. This difference is significantly attenuated with the use of statins (Figure 3). We have demonstrated that statins decrease the incidence of both stroke and eCD in asymptomatic CEA patients, eCD predicts a higher risk of early mortality compared to patients without eCD, and different gene polymorphisms have effects on the incidence of eCD through a variety of mechanisms. Additionally, we find that some statins work better than others to reduce eCD in asymptomatic patients, the efficacy of statins may be dose-dependent, and the effect of statins on asymptomatic patients having CEA is also present in patients having carotid artery stenting and endarterectomy for symptomatic stenosis.

2.2 Study Rationale

CEA reduces the risk of future stroke in this patient population by 55-65%, but its effectiveness is dependent on very low peri-operative morbidity, especially in patients presenting with asymptomatic disease. Recent improvements in the medical management of patients with asymptomatic stenosis have improved the outcome for un-operated patients to such a degree that some have even questioned whether the benefits of asymptomatic CEA still justify its risks. The rate of peri-operative stroke has fallen precipitously over the same period to less than 1.5%. It is critical that peri-operative management continue to evolve if the neuroprotective effects of CEA are to be realized for all CEA patients. Given that post-CEA stroke is so rare, investigators have increasingly looked to subtler, although more common, forms of cerebral injury to inform treatment decisions and improve procedural safety. eCD affects ~25% of patients undergoing CEA and ~15% of undergoing asymptomatic CEA. It is associated with marked elevations in tissue markers of cerebral injury (S100B) and is associated with earlier post-CEA mortality (1-3).

This clinically significant, but subtle, cerebral injury is 10 times more common than stroke and its mechanism appears to be similarly related to regional hypoperfusion and ischemia. We now have data that pre-operative statin use is not only associated with a reduction in peri-operative clinical stroke, but a 50% reduction in eCD (4). While no patient taking statins actually suffered a stroke, the rate of eCD varied dramatically among both statin type and dose. In fact, in looking at the incidence of eCD in those taking the two most commonly prescribed agents (80% of patients), simvastatin use was associated with significantly less eCD than atorvastatin(5). This difference was observed at all doses with the exception of high dose atorvastatin (80mg), which provided similar neuroprotection as high dose simvastatin (40mg). We also observed that statin use was associated with less risk of early mortality that appears to be completely related to its effect on eCD, supporting the contention that statins not only protect against injury, but may be involved in injury repair as has been shown previously in animals (6,7). As >50% of patients are on a lower dose statin regimen, it is imperative that we determine in a prospective randomized trial whether alteration/increase of preoperative statin regimens leads to improved neurologic outcome and an even lower incidence of stroke and possibly greater survival. In order to optimally design and conduct such a trial it is critical that we: 1) explore the safety and feasibility of altering statin regimen acutely (~2 weeks) before CEA, and 2) clearly establish the neuroprotective outcome of an acute alternation in statin regimen.

We think that in doing this, we will be well on our way to achieving our ultimate goal of better understanding statin neuroprotection in humans and determining the statin treatment that affords the most neuroprotection in patients undergoing one of the most commonly performed procedures in the US.

Additional support for the study rationale comes from the previous study with a cohort of asymptomatic CEA patients and regardless of statin dose or type, where it was found that ~20% of patients' not on statins had cognitive dysfunction compared to 11% of patients on statins.(72) This statistic alone leads us to believe that while a higher dose may be "more neuroprotective," any statin therapy at all will be beneficial to a patient undergoing CEA, and should become standard of care. Although we have evidence to demonstrate the efficacy of statin neuroprotection in CEA, the aim of this study is to reconfirm this and indicate that statin use

should be a standard of care preoperatively. We do not have a dose response curve and are guessing that a high dose is most beneficial. The purpose of this study is to show that. In addition, patients in the first arm of the study who are already on the high dose will be maintained, so no risk there. Patients in the second arm of the study, having already been started on statins, will just maintain the original regimen deemed appropriate by their prescribing physician or a higher, maximal dose, which we hope to demonstrate will reduce the incidence of cognitive dysfunction. Regardless of the randomization, they will be on a dose considered to be suitable for them and we believe they will experience sufficient neuroprotection peri-operatively. As for the third arm of this study, while we would have liked to randomize patients not already on a statin, to placebo or maximal high dose of atorvastatin, we think that providing a low dose may be sufficient. There is no evidence of the most effective dose of atorvastatin or any statin to provide increased benefit. These patients not already on statin therapy, will have ~2 week preoperative statin period which will afford significantly greater protection than going into CEA without any statin therapy. As no patients in this study will be entirely without statin therapy, we feel the benefit of a statin in general (versus no statin) greatly outweighs the issue of optimal (versus sub-optimal) dose.

2.2.1 Hypothesis

While there are several non-modifiable risk factors for eCD after CEA identified from previous research, including medically treated diabetes mellitus and the presence of the ApoE-ε4 genotype, we have only been able to identify one potentially neuroprotective factor, namely preoperative statin use. Consequently, we hypothesize that in CEA patients:

- 1) A pre-operative statin regimen is protective against eCD (12-25h) and dCD (30d); consequently, early (365d) mortality.
- 2) Maximal doses may be essential in achieving optimal neuroprotection against eCD and dCD, with lipophilic statins or those that pass the blood-brain barrier more easily achieve similar effects at lower doses.

3 **STUDY DESIGN**

[figure not shown]
This is a Phase 3, multicenter, observational (ARM 1), randomized and double-blind study (ARM 2 and ARM 3), and placebo-controlled (ARM 2), where 1,000 carotid stenosis outpatient participants will be assigned to a specific daily statin regimen of no fewer than 2 and no greater than 18 doses prior to their CEA.

We will include patients who are either statin naïve, assuming no history of adverse experience with a statin, or on one of three types of statins: simvastatin, atorvastatin, or rosuvastatin. Patients will be enrolled, and based on their preexisting statin regimen, they will be grouped into one of three arms prior to CEA: ARM 1) Patients on a pre-existing maximal daily dose statin regimen will be observed, ARM 2) Patients on a pre-existing statin regimen at sub-maximal doses will be randomized to maintain their current dose plus placebo or current dose plus the necessary milligrams to reach maximal daily dose, and ARM 3) Patients who are on no preexisting statin regimen, statin naïve in the last 30 days, will be randomized to atorvastatin

10mg or atorvastatin 80mg for no fewer than 2 and no greater than 18 daily doses before their CEA (Figure 6).

As per the simvastatin drug insert, patients taking amlodipine (Norvasc) should not exceed 20 mg of simvastatin; therefore, we will only potentially increase any patient who is also on amlodipine to daily doses of 20 mg and not 40 mg. Consequently:

- *If subject is on 40 mg simvastatin without amlodipine – they will be in ARM 1 (observational)
- *If subject is on 40 mg simvastatin + amlodipine – they will be in ARM 1 (observational)
- *If subject is on 20 mg simvastatin + amlodipine – they will be in ARM 1 (observational) *If subject is on < 40 mg of simvastatin without amlodipine, they will be in ARM 2 and potentially randomized to 40 mg of simvastatin daily.
- *If subject is on < 20 mg of simvastatin + amlodipine, they will be in ARM 2 and potentially randomized ONLY to 20 mg of simvastatin daily not 40 mg.

All potential participants will be pre-screened for eligibility prior to offering them participation in the study. Once informed consent has been obtained, the final screening process to screen out those who may already have mild cognitive impairment (MCI) from the study will consist of the Montreal Cognitive Assessment (MoCA ≤ 25 = abnormal) and the Ascertain Dementia 8-item Informant Questionnaire (AD8 ≥ 2 = abnormal). If both assessments are not within normal ranges, these patients will not be randomized or assigned to the observational arm. Those with baseline MCI will be screened out from the study and not followed.

All of the potentially eligible subjects will be documented in the Study Screening Log (see Appendix III) and the logs will be collected monthly by the Central Coordinating Center at CUMC.

[figure not shown]
The randomization design is stratified by center, previous use of statin and in random blocks of 4 and 6. After the participant completes the screening process, ARM 2 and ARM 3 will be randomized using a centralized, secure web-based system created and managed by the Statistical Analysis Center (SAC) at the Mailman School of Public Health at Columbia University.

The study personnel will request the study drug from the site's Pharmacy/Research Pharmacy and provide the participant with the study drug instructions and corresponding amount of study drug capsules to take during their dosing period. The participants will self-administer the assigned daily doses of study statin and keep a Study Medication Compliance form (diary) of all doses taken, including their current statin doses, and the reasons for any missed dose(s) from enrollment to the day of their CEA. On the day of CEA, the remaining study drug capsules will be counted and the Study Drug Log will be collected to assess compliance.

The participant's statin therapy after their CEA will be determined by their attending or primary care doctors and not the study physicians. The study team will inform the participant and their attending doctors. Their primary care doctor will receive a letter informing them of their patient's study participation (see Appendix V PMD letter).

The study will evaluate if the changes in statin regimen prior to CEA are neuroprotective against eCD (12-25 hours post-CEA) and dCD (30 +/- 5 days post-CEA or day of their post-CEA clinical visit) with neuropsychometric tests. The neuropsychometric tests are designed to demonstrate general neuropsychological performance and not to be diagnostic of specific neuropsychiatric disorders. The average amount of time to complete the neuropsychometric battery is 30-45 minutes. Individual subject participation will conclude Day 365 +/- 30 days post-CEA to assess morbidity and mortality (Figure 7). Consequently, the individual subject participation will be one year post CEA and the overall study completion timeline will be five years of enrollment years plus one year follow up for the last participant enrolled to complete follow up.

Figure 7: Study Participation Timeline

** follow-up calls before CEA will be conducted only if not preceded by CEA

We have defined our primary outcome on Z-scores based on the mean and standard deviation of cognitive testing change in scores of a surgical reference group before and after surgery (1225h and approximately 30 days post-op). Consequently anyone with: (a) $\geq 2SD$ worse than reference group in two or more cognitive domains or (b) $\geq 1.5SD$ worse than the reference group in all cognitive domains tested will be considered a primary outcome.

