5 STUDY INTERVENTIONS

5.1 Interventions, Administration, and Duration

The study assigned statin dosing will be taken daily for no fewer than 2 and no greater than 18 doses prior to the participant's CEA. If the encounter and enrollment happen prior to the 18 day timepoint and the patient cannot return to the study site prior to their CEA, then the subject will be given the study drug and begin taking it no greater than 18 days prior to their CEA. We will strive to enroll the subjects as early as possible so that they may receive as many doses (up to 18 doses) prior to CEA. The date of drug start will be noted in the Medication Compliance form (diary) and the eCRF upon enrollment. The safety follow-up phone calls will begin based on when the study drug is scheduled to start or upon enrollment for Arm 1. All of the participants in each arm will be provided with instructions in the Study Medication Compliance form where they will note each dose taken or the reason(s) for missing a dose. This includes logging in their current statin use for the observational/ maximal dose group (Arm 1) and the sub-maximal dose group (Arm 2). This form will be collected when the subject returns to the medical center for their CEA. The treatment arms are as follows:

ARM 1: Subjects already on **maximal daily doses** will continue to take their daily statin during the dosing period prior to CEA (atorvastatin 80 mg, simvastatin 40 mg with/without amlodipine or simvastatin 20 mg plus amlodipine, or rosuvastatin 20 mg). No additional drug will be dispensed to this group.

ARM 2: Subjects on **sub-maximal daily doses** (atorvastatin <80 mg or simvastatin <40 mg without amlodipine and <20 mg on amlodipine or rosuvastatin <20 mg) will continue to take their daily statin during the dosing period prior to CEA PLUS they will be given the corresponding study drug bottles of:

- **Atorvastatin vs Placebo (each active study capsule = 10 mg)**

- 126 capsule count bottle
 - Coordinator will write on the label how many capsules the participants need to take when they take their statin drug each day (example: If subject is currently on 10 mg of atorvastatin, then they will need to add 7 capsules/day to potentially reach 80 mg of active drug.)

- **Simvastatin vs Placebo (each study capsule = 5 mg)**

- 126 capsule count bottle
 - Coordinator will write on the label how many capsules they need to take when they take their statin drug each day (example: If subject is

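### Patients already taking simvastatin 40 mg with amlodipine enter Arm 1 above the limit the protocol quotes; no visible step alerts the treating physician, and the doctor letter can be read as discouraging a change

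*Combined protocol and SAP*

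**What the plan says.** Section 3 quotes the insert limit ("As per the simvastatin drug insert, patients taking amlodipine (Norvasc) should not exceed 20 mg of simvastatin") and draws one consequence from it: "we will only potentially increase any patient who is also on amlodipine to daily doses of 20 mg and not 40 mg". Section 5.1 describes the resulting Arm 2 cap as a safety measure.

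The list that follows in section 3 sorts simvastatin users into arms. Three entries lead to observational Arm 1: "If subject is on 40 mg simvastatin without amlodipine", "If subject is on 40 mg simvastatin + amlodipine" and "If subject is on 20 mg simvastatin + amlodipine". Section 5.1 repeats this when it defines a maximal dose as "simvastatin 40 mg with/without amlodipine or simvastatin 20 mg plus amlodipine", has Arm 1 continue its daily statin up to CEA, and dispenses no drug to that arm. Section 9.2.1 likewise keeps Arm 1 patients on their dose.

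On contact with doctors, section 3 says "The study team will inform the participant and their attending doctors" and mentions a letter to the primary care doctor. The letter (Appendix V) says patients on maximal doses, with simvastatin given as 40 mg, stay on what they take. It asks the doctor not to change the assigned dose without clinical need and to report any change made before CEA. It does not mention amlodipine.

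**The concern.** The protocol foresees a dose and co-medication pair above a limit it quotes itself, lists that pair by name, and attaches no action to it. It then writes to the patient's primary doctor in terms that lean towards leaving the dose alone and omit the one fact that might prompt a review. A doctor who already knows of the pair can act, because the letter leaves room for clinical need. A doctor who has not noticed it gets no help from the letter. What is at stake is a missed opportunity to alert the physician. No estimate, test or error rate in the trial depends on it.

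**Working it through.** There is no plan figure to reproduce, and the only arithmetic is a dose ratio. The check sets the relevant texts side by side.

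1. **Limit against assigned arm.** Quoted limit with amlodipine: 20 mg (section 3). Dose allowed in Arm 1 with amlodipine: 40 mg (sections 3 and 5.1). Ratio: 40 / 20 = 2.0. Simvastatin added by the study in Arm 1: 0 mg (section 5.1).

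2. **Does the site know of the pair?** It should. Section 3 gives the pair its own entry in the arm list, the schedule in section 6.1 has concomitant medications collected at baseline, and section 7.3 says other drugs and doses are recorded. At 40 mg the arm is the same with or without amlodipine, so sorting the patient does not itself force anyone to act on the amlodipine.

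3. **Does any existing safeguard flag it?**
   - The interaction exclusions in section 4.2 exempt patients eligible for Arm 1 and do not list amlodipine.
   - The CK and liver-enzyme screen (6.2.2), the symptom questionnaires and repeat laboratory tests, and the notice of abnormal findings to the treating physician (7.2.1) respond to results or symptoms. So does the provision in 7.1 for changing a regimen after side effects.
   - Section 7.7 makes each site's principal investigator responsible for daily safety. This is a general duty with no stated action for this pair.
   - Sections 2.2 and 7.3 describe Arm 1 as carrying little or no risk because nothing is changed. Neither considers this subgroup.

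4. **Does the line on informing doctors cover it?** "The study team will inform the participant and their attending doctors" follows a sentence on statin therapy after CEA and precedes the one on the participation letter. It does not say what the doctors are told.

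5. **Can the letter's request be read as covering Arm 1?** Yes, though not with certainty. The letter names Arm 1 patients among those taking part and then makes its request without limiting it to randomized patients. Section 3 uses the same verb for the whole trial: "carotid stenosis outpatient participants will be assigned to a specific daily statin regimen". The protocol also often uses the word for study drug, which Arm 1 does not receive.

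6. **How many patients?** This cannot be computed. Arm 1 is planned at 225. The documents give neither the split of maximal-dose users by statin nor the share on amlodipine. The earlier cohort's statin mix in section 2.1.5 is not broken down by amlodipine use.

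**The case against.** The best defence is that Arm 1 is observational by design. The plan leaves usual care alone there, and the exemption from the interaction exclusions in section 4.2 follows the same principle. Restricting the amlodipine cap to study-driven increases is therefore a consistent choice, and that part of the defence stands. Placing these patients in Arm 1 is not the fault. The remaining point is narrower: the study holds information that it treats as safety-relevant elsewhere, and its letter omits it.

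The defence also rules out several stronger readings that a reader might infer:

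- *The study exposes patients to an over-limit dose.* It does not. The dose is pre-existing therapy and nothing is dispensed.
- *The letter forbids a change.* It does not. It allows one that is clinically needed, and a dose above the labelled limit could well qualify.
- *The letter plainly addresses Arm 1 doses.* That is one fair reading. The wording may mean study drug only.
- *The study writes to the prescriber.* The letter goes to the primary doctor. The documents do not say who prescribed either drug.
- *Nobody is ever told.* The enclosed consent form cannot be seen, and section 3 promises some contact with attending doctors. Only the absence of a visible step can be claimed.

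**Conclusion.** The point holds as a minor safety-process gap. Followed as written, the visible plan leaves a foreseen pair at 2.0 times the quoted limit without a specific alert, while the letter tends, on one fair reading, to discourage a change. The conclusion assumes that the unseen consent form does not already give the warning and that the general promise to inform doctors does not in practice include it. If either does, only the wording of the letter remains to be tidied. The documents give no basis for a patient count, which could be zero, or for any statement about harm. The gap alters no planned analysis, although acting on it could affect how a few patients are classified, as set out under the fix.

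**What to change.** 1. When a patient taking more than 20 mg of simvastatin with amlodipine is identified at enrolment, the site notifies the treating physician of the combination and of the limit quoted in section 3.
2. Add one sentence to the Appendix V letter saying that the request to leave the dose unchanged does not apply to a patient taking more than 20 mg of simvastatin with amlodipine. The decision stays with the physician.

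**Cost.** One short new site step for each such patient, and one sentence in the letter. Some regimens may change before CEA, with these consequences:

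- *Reduction to 20 mg with amlodipine.* The patient still meets the Arm 1 definition in section 3. However, Primary Objective 4 compares 40 mg with lower doses at the time of surgery, so the patient moves to the lower-dose side. It also blurs the group in Primary Objective 2 that is defined by a maximal dose already in place.
- *Stopping amlodipine at 40 mg.* The patient stays in Arm 1 and on the 40 mg side of Objective 4.
- *Switching to another statin.* This would conflict with section 5.3.3 during the dosing period.

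Recording the dose at enrolment and at surgery for these patients would keep any such move visible in the analysis.
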